# 4.3.1.7 Subgroup Analyses

For a detailed description of the Subgroup Analyses, see section 4.3 .

# 4.3.2 Best Objective Response

#### 4.3.2.1 Definition

Best objective response (BoR) will be calculated based on the overall visit responses from each RECIST assessment, described in section 3.2.10. It is the best response a patient has had following randomisation, but prior to starting any subsequent cancer therapy and up to and including RECIST progression or the last evaluable assessment in the absence of RECIST progression.

# 4.3.2.2 Derivations

BoR is based on RECIST and will be determined using BICR data and investigator data until the earliest of the first progression event (including death)/last evaluable assessment in

the absence of RECIST progression or start of any subsequent cancer therapy. The denominators are consistent with those used in the ORR analysis.

BoR will be based on RECIST using the following response categories and in the following order:

- Response with categories: CR (confirmed), PR (confirmed)
- Non-response with categories:
  - SD with categories unconfirmed CR or PR, SD (>=16 weeks) and Non-CR/Non-PD (>=16 weeks)
  - NE with categories SD (<16 weeks), Non-CR/Non-PD (<16 weeks) and no baseline RECIST or post baseline RECIST assessments in the absence of death.
  - Progression with categories: RECIST progressions and death in the absence of RECIST progression

For determination of a best response of SD and Non-CR/Non-PD, the earliest of the dates contributing towards a particular overall visit assessment will be used. SD/ Non-CR/Non-PD should be recorded at least 16 weeks minus 1 week, i.e. at least 15 weeks (to allow for an early assessment within the assessment window), after randomisation. For CR/PR, the initial overall visit assessment that showed a response should use the latest of the dates contributing towards a particular overall visit assessment.

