### 3.2.10 Derivations of RECIST 1.1 Visit Responses

For all subjects, the RECIST tumour response data is used to determine each subject's visit response according to RECIST version 1.1. It is also used to determine if and when a subject has progressed in accordance with RECIST and their best objective response to study treatment.

Baseline radiological tumour assessments should be performed no more than 21 days before the start of study treatment and ideally as close as possible to the start of study treatment. Tumour assessment is conducted every 8 weeks ( $\pm 1$  week) after the start of treatment (Cycle 1 Day 1) up to 18 months, then every 12 weeks ( $\pm 1$  week) until objective disease progression as per RECIST 1.1, irrespective of treatment decisions. Treatment start date will only be used to determine tumour assessment schedule, date of randomisation will be used for analysis.

If an unscheduled assessment is performed, and the subject has not progressed, every attempt is made to perform the subsequent assessments at their scheduled visits. This schedule is followed in order to minimise any unintentional bias caused by some subjects being assessed at a different frequency than other subjects.

From the investigator's review of the imaging scans, the RECIST tumour response data is used to determine each subject's visit response according to RECIST version 1.1. At each visit, subjects are programmatically assigned a RECIST 1.1 visit response of CR, PR, SD or PD, using the information from TLs, NTLs and new lesions and depending on the status of their disease compared with baseline and previous assessments. If a subject has had a tumour assessment that cannot be evaluated then the subject is assigned a visit response of NE, (unless there is evidence of progression in which case the response is assigned as PD).

Please refer to Table 2 for the definitions of CR, PR, SD and PD.

RECIST outcomes (i.e. PFS, ORR etc.) are calculated programmatically for the site investigator data from the overall visit responses.

If there are patients with non-measurable disease or no evidence of disease assessed at baseline RECIST has been modified to allow the assessment of progression due to new lesions in subjects with no evidence of disease at baseline.

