#### 4.3.1.2 Derivations

A confirmed response of CR/PR means that a response of CR/PR is recorded at 1 visit and confirmed by repeat imaging not less than 4 weeks after the visit when the response was first observed with no evidence of progression between the initial and CR/PR confirmation visit. Data obtained up until progression, or last evaluable assessment in the absence of progression, are included in the assessment of ORR. Also only data obtained before the start of subsequent anticancer treatment (excluding radiotherapy) are included. Therefore both visits contributing to a confirmed response must be prior to progression and prior to subsequent anticancer treatment.

In the case where a subject has two non-consecutive visit responses of PR, then, as long as the time between the 2 visits of PR is greater than 4 weeks and there is no PD between the PR visits, the subject is defined as a responder. Similarly, if a subject has visit responses of CR, NE, CR, then, as long as the time between the 2 visits of CR is greater than 4 weeks, then a best response of CR is assigned.

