#### 4.3.3 Disease Control Rate

#### 4.3.3.1 Definition

Disease control rate (DCR) at 8 weeks is defined as the percentage of patients who have at least one visit response of CR or PR prior to PD without subsequent cancer therapy or have demonstrated SD or NTL response of Non-CR/Non-PD in the absence of any new lesions for patients with non-measurable disease for at least 7 weeks (i.e. 8 weeks - 1 week to allow

for an early assessment within the assessment window) after randomisation and prior to PD without subsequent cancer therapy.

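### The best-response hierarchy ranks NE, which includes evaluable SD under 16 weeks, ahead of Progression, so subjects who progress or die after a week-8 SD are tabulated as NE

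*SAP*

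**What the plan says.** Main-study SAP section 4.3.2.2 states that "BoR will be based on RECIST using the following response categories and in the following order". The list then runs: confirmed CR and PR; SD; NE; Progression. The NE step reads "NE with categories SD (<16 weeks), Non-CR/Non-PD (<16 weeks) and no baseline RECIST or post baseline RECIST assessments in the absence of death". The last step reads "Progression with categories: RECIST progressions and death in the absence of RECIST progression".

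The timing rule for SD and Non-CR/Non-PD is in the same section: "PD should be recorded at least 16 weeks minus 1 week, i.e. at least 15 weeks" after randomisation (the quoted words begin with the tail of the label Non-CR/Non-PD). Section 3.2.10 sets the scan schedule: "Tumour assessment is conducted every 8 weeks", with a window of one week either side, from Cycle 1 Day 1. Section 4.3.2.1 runs the BOR observation period through the progression visit itself.

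On later therapy, the two response sections differ. For ORR, section 4.3.1.2 says "Also only data obtained before the start of subsequent anticancer treatment (excluding radiotherapy) are included". For BOR, section 4.3.2.1 takes the best response "but prior to starting any subsequent cancer therapy", with no exception for radiotherapy; section 4.3.2.2 has none either.

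The sub-study SAP repeats the category list in its section 4.3.6.2, counting weeks from Cycle 1 Day 1. It has the same radiotherapy difference between its ORR section (4.3.5.2) and its BOR sections (4.3.6.1 and 4.3.6.2).

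**The concern.** An ordered list works by giving each subject the first category whose condition is met. An evaluable SD at week 8 is too early for the SD step but meets the NE step through its under-16-week sub-category. A subject who then progresses at week 16, or dies without RECIST progression, is already placed in NE and the Progression step is never reached.

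The words about absence of death are attached to the sub-category for subjects with no baseline or post-baseline assessment. Nothing limits the two under-16-week sub-categories to subjects who stay free of progression and death.

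At stake are the NE and Progression totals of the BOR tables, which are presented at an interim analysis and in the CSR. Documented progressors would be counted under a heading that readers take to mean lack of usable data.

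The radiotherapy wording is a smaller, separate mismatch: if radiotherapy counts as cancer therapy, a response confirmed after it contributes to ORR but not to the confirmed CR and PR rows of the BOR table.

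**Working it through.** **1. The plan's own threshold.** Section 4.3.2.2: 16 − 1 = 15 weeks from randomisation. This reproduces the stated figure.

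**2. Can a week-8 scan reach it?** The latest in-window first scan is 8 + 1 = 9 weeks after first dose. To lie 15 weeks after randomisation, first dose would have to come 15 − 9 = 6 weeks or more after randomisation. In practice, SD at the first scan always falls in the under-16-week sub-category.

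**3. Apply the list to visit sequences**, first in the SAP order and then with Progression ahead of NE:

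| Visits | SAP order | Progression before NE |
|---|---|---|
| SD week 8, PD week 16 | NE | Progression |
| SD week 9, PD week 15 | NE | Progression |
| PD week 8 | Progression | Progression |
| SD weeks 8 and 16, PD week 24 | SD | SD |
| SD week 8, no later scan, alive | NE | NE |

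Only subjects with early SD followed by progression move; the other assignments are unchanged. Death after week-8 SD without RECIST progression behaves like the first row.

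**4. How many subjects?** The SAP states no PFS median, and its expected event percentage is not legible in the public text, so this needs an assumption. Take exponential PFS with median m months, 365.25/12/7 = 4.348 weeks per month, and treat randomisation and first dose as the same day:

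- λ = ln 2 / (4.348 m) per week
- share affected = S(8) − S(16) = exp(−8λ) − exp(−16λ)

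Example, m = 3: λ = 0.6931/13.04 = 0.0531; S(8) = 0.654, S(16) = 0.427; difference 0.226.

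| Assumed median PFS | Event between weeks 8 and 16 | Of 150 randomised |
|---|---|---|
| 2 months | 24.9% | 37 |
| 3 months | 22.6% | 34 |
| 4 months | 19.8% | 30 |
| 6 months | 15.5% | 23 |
| 12 months | 9.1% | 14 |

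With x = S(8), the share is x − x², which cannot exceed 25% (at x = 0.5, a median of about 1.84 months). These are upper figures for each assumed median, because a week-8 responder who then progresses goes to the SD step as an unconfirmed response. If 5% of all subjects are of that kind, each share falls by 5 points.

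The result depends on the shape of the curve. Weibull PFS with medians of 2 to 6 months gives 12.7% to 17.4% at shape 0.7 and 17.2% to 36.5% at shape 1.5. The table follows the main-study scan schedule and does not carry over directly to the sub-study, whose section 4.3.11.2 places a scan at Cycle 1 Day 1.

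**5. Radiotherapy.** Take PR at week 8, radiotherapy at week 10, PR at week 16, no PD. ORR keeps both visits, so the subject is a confirmed responder. If radiotherapy is a cancer therapy, BOR keeps only week 8, so the subject is an unconfirmed PR under SD. The documents give no basis for a frequency.

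**The case against.** **The order may be meant only for display.** This is possible, but the SAP gives no other hierarchy. The qualifier about absence of death would also be unnecessary if Progression already ranked ahead of NE, which suggests that the order is functional. If display was intended, the derivation is undefined and still needs a sentence.

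**The information is not lost.** This stands. Section 4.3.2.3 summarises each response and non-response category, so SD under 16 weeks remains visible as its own row. A reader might infer that short stabilisations become indistinguishable from missing assessments; the table layout does not support that. What is wrong is the heading they sit under and the two totals.

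**No decision depends on it.** This also stands. NE and Progression are both non-response. ORR, DoR and PFS are derived without this ranking. The interim stopping rules in section 5 use ORR and DCR, and BOR is only presented alongside.

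**NE at visit level is a different thing.** Section 3.2.10 lets evidence of progression override NE for a single assessment. That rule does not govern the BOR category, so it shows a difference in convention, not a direct contradiction.

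**The 16-week SD minimum is a legitimate choice.** Agreed. A reader might infer a conflict with DCR, which accepts SD "for at least 7 weeks (i.e. 8 weeks - 1 week to allow" for an early assessment. But DCR is explicitly an 8-week measure analysed at one interim only, and two endpoints with different stated durations can coexist. Nor does the rule understate both SD and Progression for the same subject: under the retained 16-week minimum, the misplaced subject belongs in Progression alone.

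**Conclusion.** The point holds on the text. Under the stated order, a subject with evaluable SD at week 8 and RECIST progression or death before any SD at 15 weeks or later receives NE in place of Progression. The NE total is inflated and the Progression total understated by the same subjects. The sub-study SAP has the same fault.

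The size is an assumption, not a figure from the plan: at most about 25% (median PFS 2 months) down to 9% (12 months) under exponential PFS, less week-8 responders, and sensitive to the shape of the curve. A reader might infer that about a fifth of subjects will be misreported. Under exponential PFS, exactly 20% needs a median near 3.9 months (or about 1.0 month), and nothing in the SAP supports choosing either.

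The consequence is confined to the BOR summaries, so this is a correction that should be made before the tables are programmed. It does not threaten the primary result. The radiotherapy difference is real but of unknown, probably small, effect, and adds no weight to the ranking point.

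**What to change.** In main-study SAP section 4.3.2.2 and sub-study SAP section 4.3.6.2, make one of two equivalent changes:

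- move Progression (RECIST progression, or death without it) ahead of NE in the ordered list; or
- keep the order, and state that SD under 16 weeks and Non-CR/Non-PD under 16 weeks fall under NE only when no later RECIST progression or death has occurred within the BOR observation period.

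Keep the 16-week SD minimum and its one-week allowance. Lowering it to 7 weeks is a different choice: it would turn the example subject into SD, not Progression.

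Separately, add an exclusion for radiotherapy to the subsequent-therapy cut-off in main-study sections 4.3.2.1 and 4.3.2.2 and sub-study sections 4.3.6.1 and 4.3.6.2. Confirmed CR plus PR in each BOR table then uses the same therapy cut-off as ORR (main-study 4.3.1.2, sub-study 4.3.5.2).

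The cost is a few lines of SAP text and one derivation in each SAP. No data collection, sample size or decision rule changes.

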#### 4.3.2.3 Analysis of Best Objective Response

The number of patients with a response and non-response along with each of the response/non-response categories will be summarised.

#### 4.3.2.4 Sensitivity Analyses

As a sensitivity analysis, BOR is analysed according to 4.3.5.4 but using BICR and investigator data.

#### 4.3.2.5 Subgroup Analyses

For a detailed description of the Subgroup Analyses, see section 4.3.

#### 4.3.3 Disease Control Rate

#### 4.3.3.1 Definition

Disease control rate (DCR) at 8 weeks is defined as the percentage of patients who have at least one visit response of CR or PR prior to PD without subsequent cancer therapy or have demonstrated SD or NTL response of Non-CR/Non-PD in the absence of any new lesions for patients with non-measurable disease for at least 7 weeks (i.e. 8 weeks - 1 week to allow

for an early assessment within the assessment window) after randomisation and prior to PD without subsequent cancer therapy.

#### 4.3.3.2 Derivations

Duration of SD (weeks) is defined as: (date last evaluable assessment of SD in the absence of progression prior to subsequent cancer therapy - randomisation date +1)/7

Patients without a post-baseline tumour assessment will be considered to have no Disease Control.

#### 4.3.4 Analysis of Disease Control Rate

DCR will be analysed at Interim Analysis 2 only (see Section 5). The DCR is presented for each treatment arm non-comparatively with a two-sided 80% CI using the Clopper-Pearson (exact probability) method. Subjects that have missing overall response assessments at all visits are considered as non-responders and are therefore counted in the denominator of DCR. The analysis of DCR is based on the Interim Response Evaluable Set.

# 4.3.5 Secondary Endpoint: Duration of Response

DoR is a secondary efficacy endpoint.

#### 4.3.5.1 Definition

DoR is defined as the time from the date of first documented confirmed objective response until the date of documented progression per RECIST 1.1 as assessed by BICR or death due to any cause.

#### 4.3.5.2 Derivations

DoR (months) = (date of PFS event [progression/death] or censoring – date of first documented confirmed objective response + 1) / (365.25/12)

The end of response should coincide with the date of progression or death from any cause used for the PFS endpoint. The time of the initial response is defined as the latest of the dates contributing towards the first visit response of PR or CR. If a subject does not progress following a response, then their DoR is censored on the PFS censoring date. Only subjects who have achieved objective response (CR or PR) are evaluated for DoR.

# 4.3.5.3 Handling of Dropouts and Missing Data

DoR is calculated for the subset of subjects with confirmed objective response (CR or PR) only. Subjects without confirmed objective response are excluded from the analysis of DoR. Dropouts and missing data will be handled according to the censoring rules detailed in Section 4.3.9.2,

#### 4.3.5.4 Primary Analysis of Secondary Endpoint

Only subjects who have achieved confirmed objective response (CR or PR) are included in the summaries of DoR. The median DoR as well as landmark estimates at 6, 9, 12, 15, 18 months of DoR and two-sided 95% CI are estimated using the Kaplan-Meier method. The analysis of DoR is based on the safety analysis set.

Swimmer plots that clearly show the profile of each subject who responds are produced.

# 4.3.5.5 Sensitivity Analyses of the Secondary Endpoint

As a sensitivity analysis, DoR is analysed according to 4.3.5.4 but using the investigator assessment per RECIST 1.1.

# 4.3.5.6 Supplementary Analyses of the Secondary Endpoint

Another sensitivity analysis for DoR is performed censoring DoR at the date of the last progression-free disease assessment prior to initiation of subsequent anticancer treatment. The rationale for this sensitivity analysis is the same as outlined in 4.3.9.5.

# 4.3.5.7 Subgroup Analyses

For a detailed description of the Subgroup Analyses, see section 4.3.

# 4.3.6 Secondary Endpoint: Time to Response

Time to Response (TTR) is a secondary efficacy endpoint. The analysis of TTR is based on the safety analysis set.

#### 4.3.6.1 Definition

TTR is defined as the time from randomisation until the date of first documented objective response, which is subsequently confirmed per RECIST 1.1 as assessed by BICR.

# 4.3.6.2 Derivations

TTR (months) = (date of first confirmed objective response – date of randomisation + 1) / (365.25/12).

# 4.3.6.3 Handling of Dropouts and Missing Data

Subjects without confirmed objective response, are treated as missing for the calculation of TTR. Only subjects who have achieved confirmed objective response (CR or PR) are evaluated for TTR.

# 4.3.6.4 Primary Analysis of Secondary Endpoint

The TTR is summarised (i.e., number of subjects [%] based on the number of responders for each treatment arm) by the scheduled assessment timepoint that the response was first observed. The number of subjects with response at different disease assessment timepoints is provided. Additionally, descriptive summary statistics are presented in addition.

The median TTR and two-sided 95% CI is assessed using the Kaplan-Meier method (without censoring because all subjects have events).

#### 4.3.6.5 Sensitivity Analyses of the Secondary Endpoint

As a sensitivity analysis, TTR is analysed according to 4.3.6.4 but using the investigator assessment per RECIST 1.1.

#### 4.3.6.6 Supplementary Analyses of the Secondary Endpoint

Not applicable

#### 4.3.6.7 Subgroup Analyses

For a detailed description of the Subgroup Analyses, see section 4.3.

# 4.3.7 Secondary Endpoint: Percentage Change in target lesion tumour size

Percentage Change in target lesion tumour size is a secondary efficacy endpoint.

#### 4.3.7.1 Definition

An outcome endpoint for this study is percentage change from baseline in TL tumour size. This is based on RECIST TL measurements taken at baseline and each post-baseline assessment. Tumour size is the sum of the longest diameters (or short axis measurements for lymph nodes) of the TLs. Baseline for RECIST is defined to be the last evaluable assessment prior to randomisation.

The TL tumour size and percentage change from baseline in the sum of TL tumour size at each assessment are calculated.

#### 4.3.7.2 Derivations

Whenever TL tumour size data for the week 16 visit (note: or visit at which progression was documented if before week 16) is available then this is used in the analysis. A windowing rule is applied and follows the protocol allowed visit window, therefore RECIST scan performed within  $\pm 1$  week of the protocol scheduled visit is used for that visit. Subjects who progress before week 16 (plus 1 week allowing for a late assessment within the visit window) should have had a tumour assessment performed at the time of progression prior to study treatment discontinuation. The TL tumour size from their latest progression assessment is used instead of the week 16 assessment for these subjects

The percentage change from baseline in TL tumour size is obtained for each subject by taking the difference between the sum of the TLs at week 16 (or earlier if the patient progressed) and the sum of the target lesions at baseline divided by the sum of the TLs at baseline times 100 (i.e. [week 16 – baseline] / baseline  $\times$  100).

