#### Table 3NTL Visit Responses

To achieve 'unequivocal progression' on the basis of NTLs, there must be an overall level of substantial worsening in non-target disease such that, even in the presence of SD or PR in TLs, the overall tumour burden has increased sufficiently to merit a determination of disease progression. A modest 'increase' in the size of one or more NTLs is usually not sufficient to qualify for unequivocal progression status.

Details of any new lesions are also recorded with the date of assessment. The presence of one or more new lesions is assessed as progression.

A lesion identified at a follow up assessment in an anatomical location that was not scanned at baseline is considered a new lesion and indicates disease progression.

The finding of a new lesion should be unequivocal: i.e. not attributable to differences in scanning technique, change in imaging modality or findings thought to represent something other than tumour.

New lesions are identified via a Yes/No tick box. The absence and presence of new lesions at each visit are listed alongside the TL and NTL visit responses.

A new lesion indicates progression so the overall visit response is PD irrespective of the TL and NTL response.

If the question 'Any new lesions since baseline' has not been answered with Yes or No and the new lesion details are blank, this is not evidence that no new lesions are present, but should not overtly affect the derivation.

Symptomatic progression is not a descriptor for progression of NTLs: it is a reason for stopping study therapy and is not included in any assessment of NTLs.

Subjects with 'symptomatic progression' requiring discontinuation of treatment without objective evidence of disease progression at that time should continue to undergo tumour assessments where possible until objective disease progression is observed.

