## 4.3 Endpoint Analyses

This section covers details related to the endpoint analyses such as primary, secondary, other endpoints including sensitivity and supportive analyses.

Efficacy analyses, except for OS, are based on BICR assessments. All images are collected centrally whether scheduled or unscheduled. The imaging scans are reviewed by 2 independent radiologists using RECIST 1.1 and are adjudicated, if required. For each postbaseline visit scan, the BICR defines the overall visit response data (complete response [CR], partial response [PR], stable disease [SD], progressive disease [PD], or not evaluable [NE] depending on the status of their disease compared with baseline and previous scans by assessing TLs, non-target lesions (NTLs) and new lesions) and the relevant scan dates for each time point (i.e., for visits where response or progression is/is not identified). Subjects who have disease progression on study treatment based on progression of non-target disease, may also require submission of additional scans/images/photographs e.g., brain scan or photographs of cutaneous lesions. If a subject has had a tumour assessment that cannot be evaluated, then the subject is assigned a visit response of not evaluable (NE) (unless there is evidence of progression, in which case the response is assigned as PD). No programmatic derivation of visit response is necessary. The date of progression is provided (by each reviewer) based on the earliest of the scan dates of the component that triggered the progression. Endpoints ORR, DoR, BOR, TTR, DCR, and PFS are then derived from the scan dates and overall visit responses. Confirmation of progression is not required.

Details on the adjudication process can be found in the CSP section 8.1.1.2.

As per the sensitivity analyses, efficacy analysis, except for OS, are also based on programmatic application of RECIST 1.1. (Eisenhauer et al, 2009) to investigator assessed tumour measurements. All RECIST 1.1 assessments, whether scheduled or unscheduled, are included in the calculations. This is also regardless of whether a subject discontinues study treatment or receives another anti cancer therapy. At each visit, subjects are
programmatically assigned a RECIST 1.1 visit response of CR, PR, SD, PD, or NE depending on the status of their disease compared with baseline and previous assessments.

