#### 4.3.8.1 Definition

The TL tumour size and percentage change from baseline in the sum of TL tumour size at each assessment are calculated. The best absolute change in TL tumour size from baseline (i.e. depth of response) is the largest decrease from baseline or the smallest increase from baseline in the absence of reduction and includes all assessments:

- up to and including the first visit at which the overall visit response is PD,
- prior to death in the absence of progression,
- prior to the start of subsequent anti-cancer therapy (excluding radiotherapy);
- or up to and including the last evaluable RECIST assessment if the subject has not died, progressed or started subsequent anti-cancer therapy.

Each post-baseline disease assessment for a subject that meets the following conditions are included: all target lesions identified at baseline have measurements recorded at the current visit (i.e. they cannot be not done or not evaluable). If a lesion is recorded as  $\leq 5$  mm then this will be used in the calculations.

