# 4.3.9.2 Derivations

Whenever TL tumour size data for the week 20 visit (note: or visit at which progression was documented if before week 20) is available then this is used in the analysis. A windowing rule is applied and follows the protocol allowed visit window, therefore RECIST scan performed within  $\pm 1$  week of the protocol scheduled visit is used for that visit. Subjects who progress before week 20 (plus 1 week allowing for a late assessment within the visit window) should have had a tumour assessment performed at the time of progression prior to study treatment discontinuation. The TL tumour size from their latest progression assessment is used instead of the week 20 assessment for these subjects.

The percentage change from baseline in TL tumour size is obtained for each subject by taking the difference between the sum of the TLs at week 20 (or earlier if the patient progressed) and the sum of the target lesions at baseline divided by the sum of the TLs at baseline times 100 (i.e. [week 20 – baseline] / baseline  $\times$  100).

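### Week-16 (sub-study week-20) target-lesion change has no cut-off at subsequent anti-cancer therapy, so it can look better than the same subject's best change

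*SAP*

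**What the plan says.** **Week-16 change (main SAP 4.3.7.2).** The scan is used "Whenever TL tumour size data for the week 16 visit (note: or visit at which progression was documented if before week 16) is available". The only substitution is for progression: "The TL tumour size from their latest progression assessment is used instead of the week 16 assessment for these subjects". Section 4.3.7.3 also summarises the change at each timepoint and draws a waterfall plot with a reference line at -30%, which it ties to partial response. Neither section mentions a new anti-cancer therapy.

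**General rule (main SAP 4.3).** For investigator RECIST data the SAP keeps every assessment: "This is also regardless of whether a subject discontinues study treatment or receives another anti cancer therapy". Change in target-lesion size is among the endpoints then listed. For the BICR data, which carry the main analysis, no exclusion is stated for this endpoint.

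**Companion endpoints.** Best percentage change (4.3.8.1) admits only assessments "prior to the start of subsequent anti-cancer therapy (excluding radiotherapy", meaning that radiotherapy does not trigger the cut-off. For ORR, 4.3.1.2 says: "Also only data obtained before the start of subsequent anticancer treatment (excluding radiotherapy) are included". Best objective response (4.3.2.1) and disease control rate (4.3.3.1) also exclude data after subsequent therapy.

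**Sub-study SAP.** Section 4.3.9.2 repeats the rule: "Whenever TL tumour size data for the week 20 visit (note: or visit at which progression was documented if before week 20) is available". Best change (4.3.10.1), ORR (4.3.5.2) and best objective response (4.3.6.1) have the cut-off, and section 4.3 repeats the general inclusion rule.

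**The concern.** Two secondary endpoints built on the same lesion measurements follow different inclusion rules, and no reason is given. The week-16 value can contain the effect of a drug that is not under study, while the best value cannot. A best change that is worse than the change at one visit is incoherent on its face, and both outputs appear as waterfall plots in the same report.

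A reader who takes a bar beyond -30% as evidence of response would be looking at a scan that the response analysis excludes. The per-visit summaries have the same gap.

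**Working it through.** **1. Can a post-switch week-16 scan exist?** Yes. Main SAP 3.2.10 schedules scans every 8 weeks (±1 week) "until objective disease progression as per RECIST 1.1, irrespective of treatment decisions". Subjects who stop for symptomatic progression "should continue to undergo tumour assessments where possible until objective disease progression is observed". Table 6 provides for a new anticancer treatment before progression or death. Examples are a switch after toxicity, after symptomatic progression, or after a progression called by the investigator but not by BICR.

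**2. Who is affected?**
- Progression on the analysed assessment before week 16: the progression scan replaces the week-16 scan, which limits the problem.
- Switch before any post-baseline scan, for example at week 6 when the first scan is due at week 8 ±1: best change has no scan to use. It is missing, or imputed at +20% in the situations listed in 4.3.8.2 and 4.3.8.3. Two scan-based values cannot conflict here, but the week-16 value still reflects the next drug.
- Switch after an evaluable scan, before week 16, without progression on the analysed assessment: the two endpoints can conflict directly.

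**3. Worked example (assumed measurements).** Baseline sum 100 mm; week 8, 95 mm (stable disease); new therapy at week 10; week 16, 55 mm. The SAP's formula is (week 16 − baseline) / baseline × 100.
- Week-16 change as written: (55 − 100) / 100 × 100 = -45%.
- Best change under 4.3.8.1, where only week 8 is eligible: (95 − 100) / 100 × 100 = -5%.
- The -45% bar passes -30%, while 4.3.1.2 excludes that scan from ORR.
- With the 4.3.8.1 cut-off applied, the 55 mm scan drops out. The week-16 value is then missing, or -5% if the last pre-switch scan is shown, and it can no longer be better than the best change.

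**4. Scale.** The SAP states no figure to reproduce. Shift in an arm's mean = share who switch × average extra change among them. The documents give neither input, so both lines below are assumptions.
- 2% to 10% switch, averaging 20 to 40 points of extra shrinkage: 0.02 × 20 = 0.4 to 0.10 × 40 = 4.0 points. That involves 2 to 10 bars per 100 subjects, or 1 to 5 per 50.
- 5% to 15% switch, and only 4% to 10% of those gain 30 to 60 points while the rest gain nothing: 0.05 × 0.04 × 30 = 0.06 to 0.15 × 0.10 × 60 = 0.9 points. The 4% and 10% are the chemotherapy response rates cited in 3.2.1.

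Continued growth on the next therapy would move the mean the other way.

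**The case against.** The strongest defence is that this is a deliberate treatment-policy choice. Section 4.3 keeps investigator scans after another therapy and names this endpoint, and PFS (4.3.9.1) also counts events regardless of further treatment. On that view the two tumour-size endpoints are simply defined differently.

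This does not settle the matter. ORR and best objective response are on the same list in 4.3, yet each has its own cut-off. The main-study BICR analysis is covered only by silence. Where the SAP follows treatment policy for PFS, it says so and adds a sensitivity analysis that censors at the switch (4.3.9.5). Section 4.3.7 states no such aim, its only sensitivity analysis is by investigator assessment, and 4.3.7.5 is marked as not applicable.

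The objection on importance does stand. Section 4.3.7.3 plans descriptive statistics and plots, with no test, confidence interval or between-arm comparison. A reader might infer that the comparison of arms is biased, since the trial is open-label and switching could differ by arm. The documents give no switching rates and plan no inference on this endpoint, and the sub-study has a single arm, so the argument cannot apply there.

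**Conclusion.** The inconsistency is real in both SAPs and worth correcting. It concerns a limited group: subjects who switch after an evaluable scan, before week 16 (20), without progression on the assessment analysed. For them the week-16 bar can reflect next-line shrinkage, cross -30% with a scan that ORR excludes, and exceed the best change. That conclusion rests on the text and does not depend on how often it happens.

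The size cannot be determined from the documents and is probably small. A reader might infer a shift of several points: 5% to 15% switching with 30 to 60 points of extra shrinkage would give 0.05 × 30 = 1.5 to 0.15 × 60 = 9 points. That requires such shrinkage on average across all switchers, whereas 3.2.1 states that there is no standard of care after anti-PD-(L)1 therapy and cites response rates of 4% and 10% for later-line chemotherapy. Those rates are only a rough guide, since other agents could do better. Primary ORR is not affected.

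**What to change.** In main SAP 4.3.7.2, for the per-visit summaries in 4.3.7.3, and in sub-study 4.3.9.2 and 4.3.9.3, apply the cut-off from 4.3.8.1: only target-lesion assessments made before any subsequent anti-cancer therapy contribute, with radiotherapy not counted. Add an exception for this endpoint to the general inclusion sentence in section 4.3 of each SAP.

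For subjects who switch before week 16 (20), set that value to missing and report the number by arm (overall in the sub-study). If the sponsor prefers to show the last pre-switch post-baseline scan, label this as a new rule and leave the value missing when no such scan exists. It is not what the plan does for early progression, where the progression scan itself is used. If treatment policy is intended after all, state it and flag the affected bars.

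The cost is a sentence or two in each SAP and one date filter in programming. The downside is a few missing or earlier values.
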